For 6 weeks, during the Baseline and Treatment I & II segments:

- Daily diaries about sleep timing and quality, work hours, medication use.
- 24-h actigraphy to assess sleep duration and sleep quality

At Baseline and End of Treatment Visits (Visit 2 & 5):

- Objective sleepiness (MWT)
- Subjective sleepiness (KSS, modified ESS)
- Clinical global impression (severity and change) (CGI, CGI-S, CGI-C)
- Patient global impression (severity and change) (PGI, PGI-S, PGI-C)
- Work function and daily activity (WPAI-SHP)
- Subjective global functioning (FOSQ-10, SDS)

V.a. DETAILS OF METHODS

Actigraphy data. Actigraphy data will be collected in 60 s epochs and sleep—wakefulness will be scored in each sleep episode per epoch by MotionWare (CamNTech, Cambridge, UK) using the high-sensitivity setting. Bed and wake times will be determined from sleep diaries and input into the software for sleep—wakefulness analysis.

Total sleep time (TST) will be calculated as minutes of sleep in each sleep episode. Naps will be scored separately from nighttime sleep.

Fragmentation Index (FI) will be calculated as the sum of the "Mobile time" (percent of presumed sleep episode categorized as mobile) and the "Immobile bouts" <=1min (%)" (percentage of the total number of immobile bouts that are less than or equal to one minute).

Daily diaries. During the 2-week Baseline Segment and the 4-week Treatment Segment, the participant will complete daily sleep and work diaries. These will consist of questions about work timing, subjective work performance and sleepiness, caffeine use, napping (included in work diary and completed after work), prior night's bedtime and waketime, subjective sleep latency, number of awakenings, and soundness, reason for waketime, sleep aid use (included in sleep diary and completed after waking and before beginning work). During the Treatment Segment, we will also ask them about whether they used the study medication that day.

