For the secondary endpoints of CGI and PGI, change between the treatment group and the placebo group will be analyzed using a chi-square test.

To address the multiplicity issue due to the hypothesis testing on the primary and secondary endpoints, a fixed hierarchical testing sequence will be employed. The familywise type I error rate will be controlled at the 2-sided significance level of 0.05. The testing procedure will be stopped when the p-value of a specific endpoint exceeds the significance level of 0.05. Statistical hypotheses will be tested in the following sequential order:

- 1. the change in objective sleepiness between the Baseline MWT and the End of Treatment (EOT) MWT
- 2. the change in subjective sleepiness between the Baseline KSS and the EOT KSS
- 3. the change in clinical condition between Baseline and EOT as assessed by a physician using the CGI-C
- 4. the change in the patient's subjective report between Baseline and EOT visit as assessed by PGI-C.

The **Exploratory Endpoints** are:

- a) the change in subjective sleepiness between Baseline and EOT visit as assessed by modified ESS.
- b) the change in work function and daily activity between Baseline and EOT visit as assessed by WPAI-SHP
- c) the change in subjective global functioning between Baseline and EOT visit as assessed with FOSQ-10 and SDS.
- d) no change in objective sleep duration or sleep quality assessed by actigraphy-estimated TST and actigraphy-estimated FI, averaged across the 2 Baseline weeks compared to weeks 3+4 of Treatment.

To test the exploratory objectives, we will analyze the change from Baseline to EOT between the solriamfetol group and the placebo group by descriptive statistics, and to analyze the continuous variables using a mixed model with repeated measures analysis that will include baseline measure, treatment (solriamfetol, placebo), time (Baseline, EOT), and treatment by time interaction as fixed effects and participant as a random effect, and to analyze discrete variables using a chi-square test.

All significance tests will be 2-tailed and at p < 0.05 level.

Sample Size Justification

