The sample size estimate for the primary endpoint is based on the results of the study of solriamfetol in patients with OSA (Schweitzer, 2019). With 50 participants per group, we can detect a difference of 5.7 minutes or greater on the MWT with power of 97% (α =0.05, assumed σ =7.2). Sample size estimates for the secondary endpoints are based on the results of the study of modafinil in patients with SWD (Czeisler, 2005). With 50 participants per group, we can detect a difference as small as 0.6 points on the KSS with power of 84% (α =0.05, assumed σ =1), and a difference of 27% or greater in the proportion of patients reporting at least minimal improvement on the CGI-C with 80% power (α =0.05, assumed a placebo proportion at 49%).

The study will randomize 110 individuals and allow for a 10% dropout rate. If a participant drops out after at least 1 week on treatment, they will be encouraged to come in for an MWT visit.

VI. RISKS & DISCOMFORTS

Contraindications

Solriamfetol is contraindicated in patients receiving concomitant treatment with MAOI, or within 14 days following discontinuation of MAOI, because of the risk of hypertensive reaction.

Drug side effects and toxicities

Solriamfetol is an FDA-approved (for excessive daytime sleepiness associated with OSA and narcolepsy) medication with a robust clinical safety database comprised of healthy participants and participants with OSA, narcolepsy, Parkinson's disease, and MDD with a consistent safety profile across conditions. The robust efficacy of solriamfetol has been demonstrated among participants with OSA and narcolepsy including examination of post-hoc analysis of the subgroup of participants on concomitant antidepressants. The risks to participants in this study are expected to be similar to those seen in prior clinical studies that evaluated the effects of 75 mg and 150 mg solriamfetol in OSA and narcolepsy patients, including those on concomitant antidepressants. Current information on the efficacy, pharmacokinetic(s), and safety of solriamfetol is provided in the solriamfetol Investigator's Brochure (IB), the United States Package Insert (USPI) and the Summary of Product Characteristics (SmPC).

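### The mixed model for continuous exploratory endpoints uses baseline as both covariate and outcome row, so treatment-by-time gains nothing from baseline adjustment and its standard error depends on an unstated covariance choice

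*Combined protocol and SAP*

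**What the plan says.** Section V.b, under the exploratory endpoints, gives one model for every continuous variable, with these terms: "baseline measure, treatment (solriamfetol, placebo), time (Baseline, EOT), and treatment by time interaction as fixed effects and participant as a random effect". The aim is stated in the same sentence: "we will analyze the change from Baseline to EOT between the solriamfetol group and the placebo group by descriptive statistics", followed by the mixed model.

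There are only two time points per participant. The questionnaires are collected "At Baseline and End of Treatment Visits (Visit 2 & 5"), and actigraphic TST and FI are reduced to two means, "averaged across the 2 Baseline weeks compared to weeks 3+4 of Treatment". On testing, the section says "All significance tests will be 2-tailed and at p < 0.05 level".

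No other section removes the baseline row or the baseline covariate from this model. An unstructured covariance matrix, Kenward-Roger degrees of freedom and a 95% confidence interval are specified for the MWT and KSS models only. For the exploratory model the plan gives no covariance structure beyond the participant effect, and it does not name the contrast to be reported.

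**The concern.** Baseline can enter such a model as a covariate or as an outcome. Here it does both. In the Baseline row the outcome is regressed on itself, where the true slope is 1. In the EOT row the slope is the regression of EOT on baseline, which is usually below 1. One common slope is fitted to both rows.

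Two consequences need checking: whether the covariate still improves the precision of the treatment comparison, and whether the model's standard error is right. At stake are the p-values for modified ESS, WPAI-SHP, FOSQ-10, SDS, TST and FI, in so far as each is analysed as continuous.

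**Working it through.** **Inputs.** From the Sample Size Justification: 50 per arm and two-sided alpha 0.05. The plan gives no figure for the exploratory model, so its MWT power was reproduced to confirm n and alpha. With difference 5.7 and "assumed σ =7.2", (5.7/7.2) × √25 = 3.96, and 3.96 − 1.96 = 2.00, giving power 97.7% (97.5% by noncentral t) against 97% stated. The baseline-to-EOT correlation ρ is not in the documents; 0.3, 0.5 and 0.7 are assumed. Variances below are in units of σ² × 2/n, with complete data and equal variances at the two visits unless stated.

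**Step 1: the estimate.** The covariate is constant within a participant and cancels from the within-participant difference. The treatment-by-time estimate is therefore the raw difference in mean change. A fitted mixed model confirmed this (−0.2387 both ways). Coding the outcome as change gives the same estimate and standard error.

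**Step 2: precision.** The variance of the raw change contrast is 2(1−ρ). The ANCOVA variance is 1−ρ². The ratio is 2/(1+ρ).

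**Step 3: the reported standard error.** After adjustment, the between-participant mean square estimates (1−ρ²)/2 and the within-participant mean square estimates 1−ρ. The first is never the larger, so a participant variance held at or above zero goes to zero (99.9-100% of simulated trials at these ρ). The two are then pooled. The model variance of the contrast becomes (1−ρ)(3+ρ)/2, and reported SE / true SE = √((3+ρ)/4). At ρ = 0.5 the variances are 0.875 reported, 1.0 true and 0.75 for ANCOVA.

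| ρ | Variance vs ANCOVA | Reported/true SE | Simulated type I error |
|---|---|---|---|
| 0.3 | 2/1.3 = 1.54 | √0.825 = 0.908 | 7.1-7.7% |
| 0.5 | 2/1.5 = 1.33 | √0.875 = 0.935 | 6.7-6.9% |
| 0.7 | 2/1.7 = 1.18 | √0.925 = 0.962 | 5.5-5.8% |

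The last column is the range over three separate simulations at 50 per arm. ANCOVA held 4.7-4.8% at the same three values in 20,000 simulated trials each. For a 0.5 SD effect, simulated power was 62% / 75% / 91% for the planned contrast and 73% / 82% / 94% for ANCOVA. The planned test rejects too often under the null and still has less power.

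**Step 4: unequal spread.** Let k = EOT SD / baseline SD and b = ρk, the slope of EOT on baseline. Then reported/true variance = 1 − (1−b)² / [2(1+k²−2b)]. At ρ = 0.5:
- k = 1.3 (b = 0.65): 1 − 0.1225/2.78 = 0.956; simulated type I error 5.5%.
- k = 0.8 (b = 0.40): 1 − 0.36/1.68 = 0.786; simulated type I error 8.5%.

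The precision loss moves the same way. Its ratio is 1 + (1−b)² / [k²(1−ρ²)], which is 1.10 at k = 1.3 and 1.75 at k = 0.8.

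**Step 5: other readings of the model.**
- *Negative within-participant covariance allowed:* the standard error is correct (simulated type I error 4.6-5.2% over all settings tried), but the precision loss in step 2 remains.
- *EOT least-squares mean difference reported:* at ρ = 0.5 the common slope is (1+0.5)/2 = 0.75. The EOT residual variance is 1 + 0.5625 − 0.75 = 0.8125 and the Baseline residual variance is 0.0625. The model averages them to 0.4375. With 2/n = 0.04, the reported SE is √0.0175 = 0.132 and the true SE is √0.0325 = 0.180. Simulated type I error is 14.0-14.8% at the three ρ values.
- *Unstructured matrix carried over from the MWT and KSS models:* as the baseline coefficient approaches 1, the Baseline residuals vanish and the likelihood grows without bound (log-likelihood 154.5 at a coefficient of 0.75, 706.7 at 0.999). No valid fit exists.

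**The case against.** The strongest reply is that this is a loosely worded model for endpoints outside the error-controlled sequence. Only MWT, KSS, CGI-C and PGI-C are in the hierarchy. The exploratory measures are each tested at 0.05 without multiplicity control, beside which a move from 5% to 6-8% per test is small. In a randomised trial with complete data, the difference in mean change is unbiased. The standard-error fault also needs a constraint that the plan does not state, and it fades as the slope of EOT on baseline nears 1. The entry rule on modified ESS (scores below 11 excluded) may restrict baseline spread and push that endpoint in this direction. All of that stands, and it limits the size of the point.

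It does not rescue the model. The loss of baseline adjustment in the treatment-by-time contrast does not depend on the non-negativity constraint. None of the readings examined gives both a correct standard error and full baseline adjustment.

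A reader might infer that the standard errors are simply too small. The documents do not support that without the constraint, because no covariance structure is given. A reader might also infer that too-narrow intervals for TST and FI carry the claim that sleep is not harmed. No interval is planned for any exploratory endpoint. The objective is worded as absence of a significant reduction, with no margin, and that is a separate weakness which this model neither creates nor cures.

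**Conclusion.** The model is wrong as written, with modest consequences confined to exploratory p-values. The firm part is the lost adjustment: with complete data and equal variances, the contrast's variance is 54% / 33% / 18% above ANCOVA at ρ = 0.3 / 0.5 / 0.7. The loss is smaller when EOT spread is larger than baseline spread and greater when it is smaller.

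The conditional part is the standard error. Under a non-negative participant variance it is about 9% / 6% / 4% too small, with type I error about 7-8% / 7% / 6%. It is correct if negative covariance is allowed. Reporting the EOT least-squares mean difference would be worse, at about 14-15%. All these sizes rest on an assumed ρ and on complete data.

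The finding does not extend to the primary or secondary tests or to the stated power. The MWT and KSS models do not list their time levels, so whether they share the fault is a separate question.

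**What to change.** In section V.b, replace the model sentence for continuous exploratory variables with: the EOT value (the mean over treatment weeks 3 and 4 for TST and FI) will be analysed by ANCOVA with treatment and the corresponding baseline measure as terms, with EOT as the only outcome row.

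Alternatively, keep both rows, drop the baseline covariate, use an unstructured covariance and constrain the two arms to a common baseline mean. This version also keeps participants who have a baseline value but no EOT value.

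In either case, name the treatment contrast to be reported. The cost is one sentence, with no change to data, participants or procedures. It should be settled before treatment codes are released.

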FOSQ-10: The purpose of this questionnaire is to find out if the participant has difficulty carrying out daily activities because they are too sleepy.

SDS: This questionnaire was developed to assess functional impairment in three inter-related domains: work/school, social, and family life.

Modified ESS: This questionnaire rates the chances of the participant dozing off or falling asleep while taking part in eight different activities. The standard questionnaire refers to "in recent times". We will modify the questionnaire to ask about the past week while working early morning shifts and we will modify questions so they are related to work situations.

In addition to completing the study questionnaires, a physician will complete a Clinical Global Impression of the patient in which they are asked to rate the patient relative to their past experience with other patients with the same diagnosis (Shift Work Disorder, Excessive Daytime Sleepiness), with or without collateral information. The **CGI** is rated on a 7-point scale, with the severity of illness scale using a range of responses from 1 (normal) through to 7 (amongst the most severely ill patients). Illness severity (CGI-S) will be rated at the Baseline MWT Visit to establish a baseline for each patient and change or improvement (CGI-C) will be rated at the End of Treatment MWT to measure the patient's change (improvement or worsening) compared to baseline. The participant will self-report at the same two time points on the Patient's Severity of Illness scale (PGI-S, baseline) and change (PGI-C).

Data management and privacy. All data (PSG data, KSS data, actigraphy data, responses to questionnaires) will be collected and recorded using a study code rather than individually-identifying information. This is a routine practice in our laboratory, and we therefore have systems in place to assign a study code upon enrollment into the protocol and to use study codes on data collection systems. Study questionnaires will be collected in REDCap. All data from the study will be stored on a Partners shared file area where access will be limited to study personnel.

V.b. BIOSTATISTICAL ANALYSIS

Variables

- Daily diary about work timing, subjective work performance and sleepiness, study medication use and timing, caffeine use, napping, prior night's bedtime and waketime, subjective sleep latency, number of awakenings, and soundness, reason for waketime, sleep aid use.

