- 24-h actigraphy to assess sleep duration and sleep quality

At baseline and End of Treatment visits (visit 1 & 5):

- Objective sleepiness (MWT)
- Subjective sleepiness (KSS, ESS)
- Clinical global impression (CGI, CGI-S, CGI-C)
- Patient global impression (PGI, PGI-S, PGI-C)
- Work function and daily activity (WPAI-SHP)
- Subjective global functioning (FOSQ-10, SDS)

Analysis of objective sleepiness.

The **Primary Endpoint** of this study is the change in objective sleepiness between the Baseline MWT and the End of Treatment (EOT) MWT [average sleep latency on first 4 scheduled naps]. To test the primary hypothesis, the primary endpoint of the change in MWT from Baseline to EOT between the solriamfetol group and the placebo group will be analyzed using a mixed model repeated measures analysis that will include Baseline MWT, treatment (solriamfetol, placebo), time (as a discrete factor), and treatment by time interaction as fixed effects and participant as a random effect. An unstructured variance-covariance matrix will be used to model the correlation among repeated measurements. The degrees of freedom will be estimated by the Kenward-Roger approximation method. A 2-sided 95% confidence interval (CI) of the mean difference in MWT from Baseline to EOT between solriamfetol and placebo will be constructed.

Analysis of subjective sleepiness and clinical condition.

The **Secondary Endpoints** are:

- a) the change in subjective sleepiness between the Baseline KSS and the EOT KSS [average of the KSS given before the first 4 scheduled naps]
- b) the change in clinical condition between Baseline and EOT as assessed by a physician using the CGI-C.
- c) the change in the patient's subjective report between Baseline and EOT visit as assessed by PGI-C.

To test the secondary objectives, the secondary endpoint of the change in KSS from Baseline to EOT between the solriamfetol group and the placebo group will be analyzed using a mixed model repeated measures analysis that will include Baseline KSS, treatment (solriamfetol, placebo), time (as a discrete factor), and treatment by time interaction as fixed effects and participant as a random effect. An unstructured variance-covariance matrix will be used to model the correlation among repeated measurements. The degrees of freedom will be estimated by the Kenward-Roger approximation method. A 2-sided 95% CI of the mean difference in KSS from Baseline to EOT between solriamfetol and placebo will be constructed.

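### Does the fixed testing sequence undercut the 80% power stated for CGI-C?

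*Combined protocol and SAP*

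**What the plan says.** The Sample Size Justification in section V.b gives three powers for 50 participants per group, each with alpha 0.05:

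- MWT: 97% for a difference of 5.7 minutes with an SD of 7.2.
- KSS: "we can detect a difference as small as 0.6 points on the KSS with power of 84" per cent, with an SD of 1.
- CGI-C: "a difference of 27% or greater in the proportion of patients reporting at least minimal improvement on the CGI-C with 80% power", with a placebo proportion of 49%.

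The MWT inputs come from a solriamfetol study in sleep apnoea. For the others, "Sample size estimates for the secondary endpoints are based on the results of the study of modafinil in patients with SWD".

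Earlier in section V.b, multiplicity is handled by a fixed hierarchy: "Statistical hypotheses will be tested in the following sequential order", namely MWT, KSS, CGI-C, PGI-C. The rule is that "The testing procedure will be stopped when the p-value of a specific endpoint exceeds the significance level of 0.05". For the global impressions, "For the secondary endpoints of CGI and PGI, change between the treatment group and the placebo group will be analyzed using a chi-square test". The study randomizes 110 and allows for 10% dropout.

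**The concern.** Under the hierarchy, CGI-C can be claimed only after MWT and KSS have both reached significance. The chance of passing three tests cannot exceed the chance of passing the third alone, and is usually lower. The sample size section does not mention the hierarchy and does not say that its figures are for single endpoints. Fifty per group is also the smallest size that gives 80% for CGI-C alone, so nothing appears to be held back for the two earlier tests.

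Someone who read 80% as the probability that this trial ends with a confirmatory CGI-C claim would expect too much, by up to about 14 percentage points on one reasonable set of assumptions. If the plan had promised that probability, it would be promising something its own testing rule does not deliver.

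**Working it through.** **Inputs.** From section V.b: 50 per group; two-sided alpha 0.05; MWT difference 5.7, SD 7.2; KSS difference 0.6, SD 1; CGI-C 49% on placebo against 49% + 27% = 76%; order MWT, KSS, CGI-C. Not given anywhere: the correlation between endpoints, and whether the SDs are raw or residual after baseline adjustment.

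**Step 1: the plan's own figures.** For the means, the noncentrality is difference / (SD × √(2/n)), on 98 degrees of freedom, with critical value 1.984.

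- MWT: 5.7 / (7.2 × 0.2) = 3.958, power 97.5% (stated 97%).
- KSS: 0.6 / (1 × 0.2) = 3.000, power 84.4% (stated 84%).

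For CGI-C, with pooled proportion (0.49 + 0.76)/2 = 0.625:

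- Null SE = √(2 × 0.625 × 0.375 / 50) = 0.0968.
- Alternative SE = √((0.49 × 0.51 + 0.76 × 0.24) / 50) = 0.0930.
- Power = Φ((0.27 − 1.96 × 0.0968) / 0.0930) = Φ(0.863) = 80.6% (stated 80%). Exact enumeration of the Pearson chi-square gives 81.0%.
- At 49 per group the same formula gives 79.8%.

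All three stated powers are correct for one endpoint at a time.

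**Step 2: the chance of a CGI-C claim through the sequence.** This is P(MWT, KSS and CGI-C all significant).

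- Independent endpoints: 0.975 × 0.844 × 0.806 = 66.3%.
- Trivariate normal test statistics with an assumed common participant-level correlation: 68.6% at 0.3, 70.3% at 0.5, 72.2% at 0.7, 74.2% at 0.9, and about 75% in the limit. The limit stays below 80% because a dichotomized variable cannot correlate fully with a normal one; here the between-arm statistics are capped at 0.763.
- No assumption on dependence: at least 0.975 + 0.844 + 0.806 − 2 = 62.5%, at most the smallest single power, 80.6%.

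The same calculation for a KSS claim gives 82% to 84%, hardly different from the stated 84%.

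**Step 3: how far the Step 2 result depends on unstated inputs.** CGI-C claim, correlation 0 to 0.9 unless noted:

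| Change (assumed) | Range |
|---|---|
| None, 50 per group | 66%–74% |
| Both SDs 10% lower through baseline adjustment | 73%–78% |
| Both SDs 20% lower | 77%–80% |
| True KSS effect 0.7 | 73%–79% |
| True KSS effect 0.8 | 77%–80% |
| 52 evaluable per group, correlation 0 up to its limit | 69%–77% |
| 55 evaluable per group, correlation 0 up to its limit | 73%–80% |

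The SD rows matter because the continuous endpoints are to be "analyzed using a mixed model repeated measures analysis that will include Baseline KSS", or baseline MWT for the primary, and the plan does not say whether its SDs already reflect that. The KSS rows matter because the plan words its differences as detectable ones, not as expected effects. The last two rows matter because 110 are randomized and participants who leave after at least a week are asked back for the End of Treatment visit, where KSS and CGI-C are also collected. Evaluable numbers could therefore exceed 50 per group.

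**Step 4: what the text claims.** Each figure in the sample size section carries its own difference, its own SD or placebo proportion, and its own alpha. That is how a single-endpoint power is normally reported. No sentence links the 80% to the hierarchy or to the probability of a claim.

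**The case for a change.** The strongest counter-argument is that this plan makes a formal familywise claim and then offers secondary-endpoint powers in support of the sample size, so the power that matters for CGI-C is the one through the sequence. At the stated SDs and differences with 50 per group, no common non-negative correlation in the normal model brings that power back to 80%. There is also no slack: 110 less 10% is 99, and 49 in a group already falls just below 80% for CGI-C alone.

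The arithmetic in this stands. What does not follow is that a stated figure is wrong. The plan gives a marginal power and the objection asks for a joint one. A joint power would be useful, but the documents do not supply what is needed to state it, and any printed range would carry several added assumptions. Even the 75% ceiling relies on normal MWT and KSS, although MWT trials are cut off at 40 minutes and KSS runs from 1 to 9.

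A second objection is that the binary CGI-C analysis is only implied. Section V.a says the CGI "is rated on a 7-point scale, with the severity of illness scale using a range of responses", and the analysis text names a chi-square test without saying that categories are collapsed. That is true of the analysis paragraph. The sample size section, however, names the proportion with at least minimal improvement as the quantity compared, which supplies the missing definition. It is a matter of detail separate from power under the sequence.

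**Conclusion.** The concern does not hold. The 97%, 84% and 80% are correct single-endpoint powers, they are presented one endpoint at a time, and the plan attributes no other meaning to them. The hierarchy controls the familywise error as intended. The primary endpoint is tested first and keeps its full power, and neither the sample size nor the testing order depends on a joint power for CGI-C.

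The chance of a CGI-C claim through the sequence is indeed generally below 80%: about 66% to 75% under normal endpoints, the stated SDs taken as residual SDs, all three detectable differences true together, a binary CGI-C and exactly 50 evaluable per group. Relaxing those assumptions moves the shortfall from about 14 percentage points to essentially none. It is worth remembering when CGI-C results are interpreted, but following the plan as written gives sound results.
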